### 7.3 For CLL patients with or without Richter's transformation (Arm A and Arm C), if a patient developed progressive disease (not tumor flare) at any time of the single-agent (MK-3475) therapy, or has stable disease without partial remission at the response

evaluation at month 3 of the single-agent (MK-3475) therapy, a commercially available FDA-approved CLL signal inhibitor can be added to MK-3475 (remain at the dose 200mg IV every 3 weeks). In this clinical scenario, if the patient had not used Ibrutinib in the past, Ibrutinib is recommended to be added using the standard FDA approved dose. However, the dose of Ibrutinib can be modified by treating physician based on concomitant medications or other clinical status. If the patient had progressed or had intolerable adverse events on Ibrutinib, Idelalisib is recommended to be added using the standard FDA approved dose. The dose of Ibrutinib or Idelalisib can be reduced/adjusted due to adverse events or concomitant medications according to the package inserts of the individual agent. If the patient had used both Ibrutinib and Idelalisib in the past, it is at the discretion of investigator/treating physician to decide which FDA-approved oral CLL therapy to use according to the package inserts of the individual agent and clinical status of the patient.

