Idelalisib is metabolized primarily by CYP3A4. The AUC of Idelalisib was reduced by 75% when coadministered with a strong CYP3A inducer. Avoid coadministration with strong CYP3A inducers, such as rifampin, phenytoin, St. John's wort or carbamazepine.  
  
The AUC of Idelalisib was increased 1.8-fold when coadministered with a strong CYP3A inhibitor. If patients are taking concomitant strong CYP3A inhibitors, monitor for signs of Idelalisib toxicity. Follow dose modifications in the package insert for adverse reactions.  
  
Idelalisib is a strong CYP3A4 inhibitor. The AUC of sensitive CYP3A4 substrates was increased 5.4 fold when Idelalisib was coadministered with a sensitive CYP3A4 substrate. Avoid coadministration of Idelalisib with CYP3A4 substrates.  
  
Idelalisib also inhibits CYP2C8, CYP2C19, and UGT1A1. GS-563117 inhibits CYP2C8, CYP2C9, CYP2C19, CYP3A, and UGT1A1 in vitro. Idelalisib and GS-563117 are not likely to inhibit CYP1A1, CYP2B6, and CYP2D6.  
  
Idelalisib also induces CYP2B6, but does not induce CYP1A2 in vitro. GS-563117 does not induce these enzymes.  
  
Idelalisib and GS-563117 are substrates of P-glycoprotein (P-gp) and BCRP in vitro. Idelalisib is not a substrate of OATP1B1, OATP1B3, PAT1, OAT3, or OCT2. GS-563117 is not a substrate of OATP1B1 or OATP13.  
  
Idelalisib inhibits P-gp, OATP1B2, and OATP1B3, and GS-563117 inhibits OATP1B1, OATP1B3 in vitro. Idelalisib is not likely to inhibit BCRP, OCT2,

OAT1, or OAT3, and GS-563117 is not likely to inhibit P-gp, BCRP, OCT2, OAT1, or OAT3.

15.27 Known potential toxicities:

Warning: Fatal and serious toxicities: Hepatic, severe diarrhea/colitis, pneumonitis, and intestinal perforation. *See full prescribing information for complete boxed warning.*

**Hepatotoxicity:** ALT/AST elevations  $>5$  times ULN have occurred, and were generally observed during the first 12 weeks of therapy; transaminase elevations were reversible upon therapy interruption. Hepatotoxicity may recur upon rechallenge, even at a reduced dose; discontinue for recurrent hepatotoxicity. Avoid concomitant use with other hepatotoxic agents.

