16.326 Overall survival is defined as the time from registration to death due to any cause. The distribution of overall survival will be estimated using the method of Kaplan-Meier.

16.327 Arm A and Arm C: The overall response rate for the combination of MK-3475 and the signal inhibitor (targeted agents) will be estimated by the number of patients with an objective status of CR, CRi, nPR, CCR or PR (Arm A) or PMR, CMR, PR or CR (Arm C) while on the combination therapy divided by the total number of evaluable patients. All evaluable patients who receive the combination therapy will be used for this analysis. Exact binomial 95% confidence intervals for the true overall response rate to the combination will be calculated. In addition, the responders on this study will be further examined in an exploratory manner to determine if there are any patterns in prognostic factors or disease characteristics, including whether the patient had a Richter's transformation or Ibrutinib-resistant disease, for both single-agent MK-3475 and combination therapy responders.

16.328 Adverse Events: All eligible patients that have initiated treatment will be considered evaluable for assessing adverse event rate(s). The maximum grade for each type of adverse event will be recorded for each patient, and frequency tables will be reviewed to determine patterns. Additionally, the relationship of the adverse event(s) to the study treatment will be taken into consideration. Adverse events will be evaluated for single-agent MK-3475 in each arm and also for the combination of MK-3475 and the signal inhibitor in Arm A and Arm C.

16.33 Correlative Analyses:

16.331 PD-1, PD-L1 and PD-L2 will be measured for each patient at baseline and during treatment. Each measure will be summarized descriptively by median, min, max and interquartile range. Overall response and complete response will be correlated with each measure using Wilcoxon rank sum test. The relationship between each measure and time to event measures (DR, TNT, PFS) will be evaluated using Cox proportional hazard models.

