16.332 Markers of immune modulation and immune profiles will be summarized descriptively by median, min, max, and interquartile range (continuous factors) or frequency distribution (categorical factors) at each time point. Patterns over time will be summarized by absolute difference or relative change. Changes across time will be assessed using paired analyses, including Wilcoxon signed rank tests for continuous measures and McNemar's tests for categorical measures. Overall response and complete response will be correlated with continuous factors using Wilcoxon rank sum tests. Jitplots will be used to visually examine differences between groups for continuous factors. Overall response and complete response will be correlated with categorical factors using Fisher's exact tests.

16.34 Over Accrual: If more than the target number of patients are accrued, the additional patients will not be used to evaluate the stopping rule or used in any decision making processes; however, they will be included in final endpoint estimates and confidence intervals.

16.4 Safety Analysis Phase (Arm A and B only):

A safety analysis will be performed after the first 12 patients (6 each arm for Arm A and B) have been accrued to the study. Accrual will be temporarily halted while these patients are followed for one cycle to assess adverse events. If 2 or more of the first 6 patients in either arm experience a DLT as defined below, then accrual will continue to be temporarily suspended to the arm affected. All toxicity data will be reviewed by the study team and a decision will be made about whether the starting dose needs to be adjusted or the protocol should be continued.

Toxicity will be measured per NCI-CTCAE version 4. DLT is defined as an adverse event possibly, probably, or definitely related to study treatment that meets one of the following:

- hepatic toxicity defined as AST or ALT  $> 5 - 10 \times$  ULN for  $> 4$  weeks; Total bilirubin  $> 5 \times$  ULN for  $> 4$  weeks ; Concurrent AST or ALT  $> 3 \times$  ULN and total bilirubin  $> 2 \times$  ULN (excluding liver involvement by CLL or lymphoma) for  $> 4$  weeks (potential Hy's Law case)
- grade 4 non-hematological toxicity[except weight loss or fatigue or laboratory abnormalities not associated with clinical sequelae] lasting longer than 4 weeks despite of holding therapy and supportive treatments
- Any grade 5 AE

16.5 Data & Safety Monitoring:

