16.51 The principle investigator(s) and the study statistician will review the study at least twice a year to identify accrual, adverse event, and any endpoint problems that might be developing. The Mayo Clinic Cancer Center (MCCC) Data Safety Monitoring Board (DSMB) is responsible for reviewing accrual and safety data for this trial at least twice a year, based on reports provided by the MCCC Statistical Office.

16.52 Adverse Event Stopping Rules (to be evaluated in each arm independently for single-agent MK-3475 and separately for combination therapy): The stopping rules specified below are based on the knowledge available at study development. We note that the Adverse Event Stopping Rule may be adjusted in the event of either (1) the study re-opening to accrual or (2) at any time during the conduct of the trial and in consideration of newly acquired information regarding the adverse event profile of the treatment(s) under investigation. The study team may choose to suspend accrual because of unexpected adverse event profiles that have not crossed the specified rule below.

Single-agent MK-3475: Accrual will be temporarily suspended to the affected arm if at any time we observe events considered at least possibly related to study treatment during cycles with single-agent MK-3475 (i.e. an adverse event with attribute specified as "possible," "probable," or "definite") that satisfy one of the following:

- If 4 out of the first 12 treated patients experience a DLT as defined in Section 16.4

- If after the first 12 patients have been treated, 30% of all patients experience a DLT as defined in Section 16.4.

Combination of MK-3475 and signal inhibitor (Ibrutinib or Idelalisib) in Arm A and Arm C: Initiation of treatment with the combination (addition of Ibrutinib or Idelalisib) will be halted in Arm A and Arm C if at any time we observe events considered at least possibly related to study treatment during cycles with the combination (i.e. an adverse event with attribute specified as “possible,” “probable,” or “definite”) that satisfy one of the following:

- If 2 out of the first 6 treated patients experience a DLT as defined in Section 16.4
- If after the first 6 patients have been treated, 30% of all patients experience a DLT as defined in Section 16.4.

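### The combination-phase stopping rule and adverse-event summary pool ibrutinib with idelalisib, which weakens detection of a toxicity specific to one partner drug; results should also be tabulated by drug

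*Combined protocol and SAP*

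**What the plan says.** Section 16.52 describes its adverse-event rules as "to be evaluated in each arm independently for single-agent MK-3475 and separately for combination therapy". For the combination there are two triggers: "If 2 out of the first 6 treated patients experience a DLT as defined in Section 16.4", and "If after the first 6 patients have been treated, 30% of all patients experience a DLT as defined in Section 16.4". Neither separates the two inhibitors. The action is also joint: "Initiation of treatment with the combination (addition of Ibrutinib or Idelalisib) will be halted in Arm A and Arm C". The event counted comes from section 16.4, where "DLT is defined as an adverse event possibly, probably, or definitely related to study treatment that meets one of the following"; the count makes no attribution to an individual drug.

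The analysis follows the same grouping. Section 16.328 says "Adverse events will be evaluated for single-agent MK-3475 in each arm and also for the combination of MK-3475 and the signal inhibitor", and Goal 2.24 is the safety of MK-3475 with either inhibitor.

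Elsewhere the protocol treats the inhibitors as different regimens. Under section 7.3, "if the patient had not used Ibrutinib in the past, Ibrutinib is recommended to be added", while patients who progressed on or could not tolerate ibrutinib are directed to idelalisib, and those who have had both may receive another approved oral CLL agent. Sections 3.32 and 3.33 apply to idelalisib only. Section 15.27 carries for idelalisib a "Warning: Fatal and serious toxicities: Hepatic, severe diarrhea/colitis, pneumonitis, and intestinal perforation". Note 1 under the section 8.3 table asks that MK-3475 or idelalisib be considered as the cause of enterocolitis or pneumonitis when both are in use.

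**The concern.** One denominator serves two regimens whose risks, on the protocol's own account, differ. If one partner drug is the problem, patients on the other drug add to the denominator but few events to the numerator, so the only numeric trigger for the combination phase responds less readily. When it does respond, it stops new starts of both drugs, including one whose own record may be clean.

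The drug is chosen by treatment history, so the mix is neither fixed nor random. A pooled adverse-event rate therefore describes whatever mix happened to occur. It cannot be read as the rate for either regimen, which is what a reader of the Goal 2.24 result would want.

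**Working it through.** The documents give boundaries for the combination rule but no operating characteristics, so there is no stated figure to reproduce.

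**Inputs from the documents.** Boundaries: 2 of the first 6, then 30% (16.52). Planned accrual: 23 + 1 = 24 in Arm A and 20 in Arm C (16.12), so at most 44 patients could reach the combination. The actual number is not stated, nor is the idelalisib share.

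**Assumed inputs.** N = 20 combination patients (also 8, 12 and 30); DLT rate 40% on idelalisib and 5% on ibrutinib (also 20% and 5%); idelalisib share s of 25%, 33%, 50% and 75%, with drugs arriving in random order. The only rate given for the toxicities in the 15.27 warning is 14% for severe diarrhoea or colitis, which is not a rate of DLTs as 16.4 defines them.

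**Step 1, events needed.** After patient 6 the rule needs the smallest whole number not below 0.30 × n: 3 at n = 7 to 10, 4 at 11 to 13, 5 at 14 to 16, 6 at 17 to 20, and 9 at 30.

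**Step 2, limiting case.** Suppose every idelalisib patient has a DLT and no ibrutinib patient does. Then 2 of 10 is 20%, 5 of 20 is 25% and 8 of 30 is 27%, all below 30%. The rule stays silent provided that fewer than two of those DLTs fall in the first 6 and the idelalisib share remains below 30% throughout. Two DLTs in the first 6 meet it at once.

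**Step 3, pooled rule.** The DLT probability for a random combination patient is p = 0.40s + 0.05(1 − s). At s = 25%, p = 0.100 + 0.0375 = 0.1375. The first trigger fires with probability 1 − (1 − p)^6 − 6p(1 − p)^5 = 1 − 0.412 − 0.394 = 0.19. Adding the 30% check after each patient from 7 to 20, by exact recursion on the DLT count, gives 0.25.

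**Step 4, idelalisib counted alone.** The same thresholds are applied to the M idelalisib patients with p = 0.40, averaged over M ~ Binomial(20, s). For example, M = 5 gives 1 − 0.6^5 − 5(0.4)(0.6^4) = 1 − 0.078 − 0.259 = 0.66, and M = 6 gives 0.77.

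| Idelalisib share (N = 20) | p pooled | Pooled rule fires | Idelalisib alone |
|---|---|---|---|
| 25% | 0.138 | 0.25 | 0.59 |
| 33% | 0.167 | 0.35 | 0.72 |
| 50% | 0.225 | 0.56 | 0.85 |
| 75% | 0.313 | 0.81 | 0.91 |

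A simulation agrees to within 0.01 (0.26 and 0.82 for the pooled rule at the two ends).

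**Step 5, sensitivity at a 25% share.** Pooled against idelalisib alone: 0.20 and 0.19 at N = 8; 0.24 and 0.34 at N = 12; 0.26 and 0.76 at N = 30. With DLT rates of 20% and 5% at N = 20: 0.11 and 0.24.

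**Step 6, the joint halt.** At 60% and 75% idelalisib (N = 20, 40% and 5%), new ibrutinib starts are halted with probability 0.68 and 0.81 under the pooled rule. On ibrutinib's own record the same thresholds would be met with probability 0.03 and 0.02.

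**Step 7, price of reading the rule by drug as well.** If both true rates are 10% and N = 20, the chance of any halt rises from 0.14 to 0.23 at a 25% share and to 0.26 at a 50% share. If both are 5%, it rises from 0.04 to 0.07 at a 25% share.

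**The case against.** The strongest reply is that section 16.52 is internally consistent and is not the only protection. The rule may be adjusted at any time in light of new adverse-event information, the study team may suspend accrual below the boundary, and the investigators with the statistician, and separately the DSMB, review the study at least twice a year. Sections 8.2 and 8.3 call for discussion with the study chair when attribution is unclear, and grade 4 and 5 events judged unrelated are re-checked. All of this stands. None of it is specified by partner drug, however, and the discretion to suspend is worded for accrual and for unexpected profiles, whereas the idelalisib toxicities are already listed and the combination decision concerns initiation.

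The illustration also rests on assumptions. Section 16.21 expects patients resistant to novel agents, so idelalisib could be the larger group, and at 75% most of the detection gap closes. Arm A is closed to accrual, so the combination group may be small, and at N = 8 with a 25% share the gap is absent. The 40% rate has no source, and the DLT definition is narrow. At 20% against 5% a per-drug reading would also usually miss the excess.

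A reader might infer more than the documents support:

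- **That the pooled rule cannot fire for an idelalisib toxicity.** Step 2 guarantees this only when the idelalisib share stays below 30%, fewer than two DLTs fall in the first 6, and ibrutinib patients have none. Otherwise pooling lowers the probability without removing it.
- **That a trigger takes patients off both drugs.** The text halts new starts of the combination and does not say that patients already on it stop.
- **That section 16.328 rules out a by-drug table.** It is silent on the matter.

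**Conclusion.** The point holds as a weakness of design and reporting, not as an error or contradiction in the arithmetic. Section 16.52 uses one count and one action for two regimens that the protocol allocates differently and describes as carrying different risks, and section 16.328 plans no separation. Under the stated assumptions at N = 20, pooling costs between 0.34 of detection probability at a 25% idelalisib share (0.59 − 0.25) and 0.10 at 75% (0.91 − 0.81). The loss disappears with very few idelalisib patients. The direction is secure whenever there are enough idelalisib patients to count; the size is illustrative, because the number of combination patients, the drug mix and the DLT rates are not in the documents. The dependence of the pooled adverse-event rate on the mix needs none of these assumptions beyond unequal rates.

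The figures do not show that a particular per-drug boundary should be adopted. That is a trade-off against false halts (Step 7), and merely adding per-drug counts while keeping the pooled rule as written would still halt both drugs whenever the pooled rule is met. A by-drug tabulation carries no such cost.

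**What to change.** In section 16.328, and in the safety reports prepared for the study team and DSMB under section 16.51, tabulate combination DLTs and adverse events by partner drug (ibrutinib, idelalisib, and any other agent allowed by 7.3) beside the pooled table, with the number treated on each.

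Ask the sponsor and DSMB to reconcile the pooled count and joint halt in 16.52 with the drug-specific risks in 15.27 and note 1 under 8.3, and to state whether Arms A and C are counted together for the combination. Whether there should be a per-drug boundary, and what it would halt, is theirs to decide.

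The cost is one extra table split and a clarifying statement. The Appendix VI diary already identifies ibrutinib or idelalisib; it has no line for another agent, so that category would need to be captured. The drawback is small denominators per drug, so the by-drug rates will be imprecise and should be shown as counts over numbers treated.

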16.7 Inclusion of Women and Minorities

16.71 This study will be available to all eligible patients, regardless of race, gender, or ethnic origin.

16.72 There is no information currently available regarding differential effects of this regimen in subsets defined by race, gender, or ethnicity, and there is no reason to expect such differences to exist. Therefore, although the planned analysis will, as always, look for differences in treatment effect based on racial and gender groupings, the sample size is not increased in order to provide additional power for subset analyses.

16.73 The geographical region served by MCCC has a population which includes approximately 3% minorities. Based on prior MCCC studies involving similar disease sites, we expect about 3-5% of patients will be classified as minorities by race and about 30% of patients will be women. Expected sizes of racial by gender subsets are shown in the following table:

Accrual Estimates by Gender/Ethnicity/Race

Ethnic Category	Sex/Gender			
	Females	Males	Unknown	Total
Hispanic or Latino	0	2	0	2
Not Hispanic or Latino	20	46	0	66
Ethnic Category: Total of all subjects*	20	48	0	68
Racial Category				
American Indian or Alaskan Native	0	0	0	0
Asian	0	0	0	0
Black or African American	0	2	0	2
Native Hawaiian or other Pacific Islander	0	0	0	0
White	20	46	0	66
Racial Category: Total of all subjects*	20	48	0	68

Ethnic Categories: Hispanic or Latino – a person of Cuban, Mexican, Puerto Rico, South or Central American, or other Spanish culture or origin, regardless of race. The term “Spanish origin” can also be used in addition to “Hispanic or Latino.”  
 Not Hispanic or Latino

Racial Categories: American Indian or Alaskan Native – a person having origins in any of the original peoples of North, Central, or South America, and who maintains tribal affiliations or community attachment.  
 Asian – a person having origins in any of the original peoples of the Far East, Southeast Asia, or the Indian subcontinent including, for example, Cambodia, China, India, Japan, Korea, Malaysia, Pakistan, the Philippine Islands, Thailand, and Vietnam. (Note: Individuals from the Philippine Islands have been recorded as Pacific Islanders in previous data collection strategies.)  
 Black or African American – a person having origins in any of the black racial groups of Africa. Terms such as “Haitian” or “Negro” can be used in addition to “Black or African American.”  
 Native Hawaiian or other Pacific Islander – a person having origins in any of the original peoples of Hawaii, Guam, Samoa, or other Pacific Islands.  
 White – a person having origins in any of the original peoples of Europe, the Middle East, or North Africa.

## 17.0 Pathology Considerations/Tissue Biospecimens:

### 17.1 Summary Table of Research Tissue Specimens to be Collected for this Protocol

Pathology Review/ Correlative Study	Mandatory or Optional	Type of Tissue/ Slides to Collect	Block, Slides, Core, etc. (# of each to submit)	Visit 1: Baseline	Visit 2: At Progression	Specific details for the submission
Pathology review: Confirm diagnosis	Mandatory for non-mayo sites	H & E, stained slides	All H&E stained diagnostic slides,	X		17.2
Correlative Study:	Mandatory	Paraffin	Tissue block ( preferred ) or unstained slides (18 slides), 4-5 microns each	X	X	17.3

### 17.2 Diagnostic Slides from Original and /or Recurrent Tissue to confirm diagnosis

Central pathology review is not required as long as the tissue diagnosis of lymphoma was confirmed by a Mayo pathologist or other academic centers. If the tissue diagnosis is not confirmed by a Mayo pathologist/other academic centers, the slides will need to be reviewed to confirm the diagnosis. Completion of central pathology review is not required prior to registration; however materials for central review must be reviewed within 42 days after registration.

17.21 Central pathology review will be conducted as needed for confirmation of diagnosis by [REDACTED] and colleagues at Mayo Clinic Rochester if the initial tissue biopsy was not performed and evaluated at Mayo Clinic/other academic centers.

